5.4.5. Management of Immune-Related Adverse Events

Adverse events of a potential immunologic etiology or irAEs may be defined as an AE consistent with an immune phenomenon associated with drug exposure after all other etiologies have been eliminated. Immune-related AEs may be expected based on the nature of the study treatment, their mechanism of action, and reported experience with these and other immunotherapies. If an irAE is suspected, efforts should be made to rule out neoplastic, infectious, metabolic, toxin, or other etiologic causes before categorizing an AE as an irAE. Subjects who develop a \geq Grade 2 irAE should be discussed immediately with the sponsor.

Elevations in amylase or lipase that are \geq Grade 3 do not require dose interruption or reduction if the subject is asymptomatic or if the elevation is clinically insignificant or has been discussed with the medical monitor.

Subjects should receive appropriate supportive care measures as deemed necessary by the treating investigator. Suggested measures for the management of drug-related AEs with potential immunologic etiology are outlined in [Table 10](#). Detailed management guidelines for specific irAEs can be found in Section [5.4.5.1](#) through Section [5.4.5.7](#) and [Appendix B](#). For each AE, attempts should be made to rule out other causes, including, but not limited to, metastatic disease or bacterial or viral infection, which might require specific supportive care.

Table 10: General Guidelines for Immune-Related Adverse Events

irAE	Guidance for Interrupting or Discontinuing Study Treatment	Guidance for Restarting Study Treatment	Supportive Care
Grade 1	No action.	Not applicable.	Provide symptomatic treatment.
Grade 2	May withhold study treatment per investigator's discretion.	
May resume treatment if improves to Grade \leq 1 within 6 weeks. If AE resolves within 4 weeks, subject may restart at the same dose and schedule.
 
For an AE that does not resolve within 4 weeks, epacadostat should be reduced 1 dose level^a, but nivolumab and ipilimumab (Treatment Group A) or lirilumab (Treatment Group B) will be restarted at the same dose and schedule. If AE does not resolve within 6 weeks, study treatment with all study drugs should be discontinued or discussed with medical monitor.
	Consider systemic corticosteroids in addition to appropriate symptomatic treatment.
Grade 3	
Withhold study treatment until AE improves to Grade \leq 1.
 
Discontinue if unable to reduce corticosteroid dose to < 10 mg/day of prednisone or equivalent within 6 weeks of toxicity.
	
Any restart of study treatment must be discussed with medical monitor. Epacadostat should be reduced 1 dose level after AE has resolved to Grade \leq 1.
	
Systemic corticosteroids are indicated in addition to appropriate symptomatic treatment. May use 1 to 2 mg/kg prednisone or equivalent per day.
 
Steroid taper should be considered once symptoms improve to \leq Grade 1 and tapered over at least 4 weeks in most cases.

Grade 4	Discontinue study treatment. ^a	Not applicable. Any exceptions require medical monitor approval.	
Systemic corticosteroids are indicated in addition to appropriate symptomatic treatment. May use 1 to 2 mg/kg prednisone or equivalent per day.
 
Steroid taper should be considered once symptoms improve to \leq Grade 1 and tapered over at least 4 weeks in most cases.

^a See Section 5.4.8 for study treatment withdrawal criteria.

Note: Detailed management guidelines for specific irAEs can be found in Sections 5.4.5.1 through 5.4.5.7.

5.4.5.1. Procedures and Guidelines for Pneumonitis

All study treatment should be interrupted in subjects with symptomatic pneumonitis and an immediate evaluation should be performed. The evaluation may include bronchoscopy to rule out other causes such as infection. If the subject is determined to have study drug-associated pneumonitis, the recommended treatment plan is detailed in [Table 11](#).

Table 11: Guidelines for Management of Noninfectious Pneumonitis

Study Drug(s) Associated Pneumonitis	Withhold/Discontinue Nivolumab and Epacadostat	Guidance for Restarting Study Treatment	Supportive Care
Grade 1 (asymptomatic)	No action.	Not applicable.	Intervention not indicated.
Grade 2	Withhold study treatment.	
First episode of pneumonitis:
 
 If improves to near baseline: 
 Decrease the dose of epacadostat by 1 dose level; for nivolumab and ipilimumab (Treatment Group A) or lirilumab (Treatment Group B), restart at same dose and schedule subsequent cycles. If not improved after 2 weeks or worsening permanently discontinue all study treatment. 
Second episode of pneumonitis:
 
 Permanently discontinue all study treatment if, upon rechallenge, subject develops pneumonitis \geq Grade 2. 	Systemic corticosteroids are indicated. Taper if necessary.
Grade 3 and 4	Discontinue study treatment.	Not applicable. Any exceptions require medical monitor approval.	Systemic corticosteroids are indicated. The use of infliximab may be indicated as appropriate. See to Appendix B for additional recommendations.

Note: See [Appendix B](#) for additional guidance regarding management of noninfectious pneumonitis.

5.4.5.2. Procedures and Guidelines for Enterocolitis

Subjects should be carefully monitored for signs and symptoms of enterocolitis (such as diarrhea, abdominal pain, mucus or blood in stool, with or without fever) and of bowel perforation (such as peritoneal signs and ileus). In symptomatic subjects, infectious etiologies should be ruled out and endoscopic evaluation should be considered for persistent or severe symptoms. All study treatment should be interrupted immediately for Grade \geq 2 enterocolitis. Recommendations for management of enterocolitis are shown in [Table 12](#), as well as additional information in [Appendix B](#).

Table 12: Guidelines for Management of Enterocolitis

Study Drug(s) Associated Enterocolitis	Withhold/Discontinue Nivolumab and Epacadostat	Guidance for Restarting Study Treatment	Supportive Care
Grade 1	No action.	Not applicable.	All subjects who experience diarrhea should be advised to drink liberal quantities of clear fluids. If sufficient oral fluid intake is not feasible, fluid and electrolytes should be substituted via IV infusion. An antidiarrheal can be started.
Grade 2	Withhold study treatment.	
May return to treatment if improves to \leq Grade 1. If AE resolves within 4 weeks, subject may restart at the same dose and schedule for both nivolumab and ipilimumab (Treatment Group A) or lirilumab (Treatment Group B).
 
For an AE that resolves to \leq Grade 1 between 4 and 6 weeks after onset, epacadostat should be reduced 1 dose level, but nivolumab and ipilimumab (Treatment Group A) or lirilumab (Treatment Group B) may be restarted at the same dose and schedule. If AE does not resolve to \leq Grade 1 within 6 weeks, all study treatment should be discontinued or discussed with medical monitor.
	An antidiarrheal should be started. If symptoms are persistent for $>$ 1 week, systemic corticosteroids should be initiated (eg, 0.5-1 mg/kg per day of prednisone or equivalent). When symptoms improve to \leq Grade 1, corticosteroid taper should be started and continued over at least 1 month.
Grade 3 and 4	Discontinue study treatment.	Not applicable. Any exceptions require medical monitor approval.	Treatment with systemic corticosteroids should be initiated at a dose of 1 to 2 mg/kg per day of prednisone or equivalent. Systemic corticosteroids are indicated. The use of infliximab may be indicated as appropriate. When symptoms improve to \leq Grade 1, corticosteroid taper should be started and continued over at least 1 month.

Note: See [Appendix B](#) for additional guidance regarding management of enterocolitis.

5.4.5.3. Procedures and Guidance for Hepatitis

Liver chemistry tests (hepatic transaminase and bilirubin levels) should be monitored and signs and symptoms of hepatotoxicity should be assessed before each dose of nivolumab and epacadostat. In subjects with hepatotoxicity, infectious or malignant causes should be ruled out and frequency of LFT monitoring should be increased until resolution. Recommendations for management of hepatitis are shown in [Table 13](#) as well as additional information for management and follow-up in [Appendix B](#).

Table 13: Recommended Approach for Handling Hepatitis

Study Drug(s) Associated Hepatitis	Withhold/Discontinue Nivolumab and Epacadostat	Guidance for Restarting Study Treatment	Supportive Care
Grade 1	No action.	Not applicable.	Increase frequency of LFT monitoring to twice per week until LFTs return to baseline, or consult with medical monitor. Note: Twice weekly testing is not required for subjects with Grade 1 LFT values at baseline until Grade ≥ 2 LFT elevations are observed.
Grade 2	Withhold study treatment.	If AE resolves to \leq Grade 1 or baseline within 4 weeks, subject may restart at the same dose and schedule for both nivolumab and ipilimumab (Treatment Group A) or lirilumab (Treatment Group B). For an AE that resolves to \leq Grade 1 between 4 and 6 weeks after onset, epacadostat should be reduced 1 dose level, but nivolumab and ipilimumab (Treatment Group A) or lirilumab (Treatment Group B) may be restarted at the same dose and schedule. If AE does not resolve to \leq Grade 1 within 6 weeks, all study treatment should be discontinued.	Increase frequency of LFT monitoring to twice per week until LFTs return to baseline. If elevation persists for > 1 week, systemic corticosteroids should be initiated (eg, 0.5 mg/kg per day of prednisone or equivalent). When symptoms improve to \leq Grade 1, corticosteroid taper should be started and continued over at least 1 month.
Grades 3 and 4	Discontinue study treatment.	Not applicable. Any exceptions require medical monitor approval.	Increase frequency of LFT monitoring to every 1-2 days. Treatment with systemic corticosteroids should be initiated at a dose of 1 to 2 mg/kg per day of prednisone or equivalent. When symptoms improve to \leq Grade 1, corticosteroid taper should be started and continued over at least 1 month.

Note: See [Appendix B](#) for additional guidance regarding management of hepatitis.

5.4.5.4. Procedures for Immune-Mediated Dermatitis

Monitor subjects for signs and symptoms of dermatitis such as rash and pruritus. Unless an alternate etiology has been identified, signs or symptoms of dermatitis should be considered immune mediated. Recommendations for management of dermatitis are shown in [Table 14](#) as well as additional information for management and follow-up in [Appendix B](#).

Table 14: Recommended Approach for Handling Dermatitis

irAE	Withhold/Discontinue Nivolumab and Epacadostat	Guidance for Restarting Study Treatment	Supportive Care
Grade 1	No action.	Not applicable.	For mild to moderate dermatitis, such as localized rash and pruritus, treat symptomatically. Administer topical or systemic corticosteroids if there is no improvement of symptoms within 1 week.
Grade 2	No action.	Not applicable.	For mild to moderate dermatitis, such as localized rash and pruritus, treat symptomatically. Administer topical or systemic corticosteroids if there is no improvement of symptoms within 1 week.
Grades 3 and 4	Withhold study treatment in subjects with moderate to severe signs and symptoms of rash. Permanently discontinue study treatment in subjects with Stevens-Johnson syndrome, toxic epidermal necrolysis, or rash complicated by full thickness dermal ulceration or by necrotic, bullous, or hemorrhagic manifestations.	If AE resolves to baseline within 4 weeks, subject may restart at the same dose and schedule for both epacadostat and nivolumab and ipilimumab (Treatment Group A) or lirilumab (Treatment Group B). For an AE that resolves to \leq Grade 1 between 4 and 6 after onset, epacadostat should be reduced 1 dose level, but nivolumab and ipilimumab (Treatment Group A) or lirilumab (Treatment Group B) may be restarted at the same dose and schedule. If AE does not resolve to \leq Grade 1 within 6 weeks, all study treatment should be discontinued or discussed with medical monitor.	Administer systemic corticosteroids at a dose of 1 to 2 mg/kg per day of prednisone or equivalent. When dermatitis is controlled, corticosteroid tapering should occur over a period of at least 1 month.

Note: See [Appendix B](#) for additional guidance regarding management of dermatitis.

5.4.5.5. Procedures for Immune-Mediated Neuropathies

Subjects should be monitored for symptoms of motor or sensory neuropathy such as unilateral or bilateral weakness, sensory alterations, or paresthesia. Recommendations for management of neuropathies are shown in [Table 15](#) as well as additional information for management and follow-up in [Appendix B](#).

Table 15: Recommended Approach for Handling Neuropathies

irAE	Withhold/Discontinue Nivolumab and Epacadostat	Guidance for Restarting Study Treatment	Supportive Care
Grade 1	No action.	Not applicable.	Provide symptomatic treatment.
Grade 2	May withhold study treatment.	If AE resolves to \leq Grade 1 or baseline within 4 weeks, subject may restart at the same dose and schedule for epacadostat, nivolumab and ipilimumab (Treatment Group A) or lirilumab (Treatment Group B). For an AE that does not resolve within 4 weeks, epacadostat should be reduced 1 dose level but nivolumab ipilimumab (Treatment Group A) or lirilumab (Treatment Group B) may be restarted at the same dose and schedule. If AE does not resolve within 6 weeks, study treatment with both study drugs should be discontinued or discussed with medical monitor.	Consider systemic corticosteroids in addition to appropriate symptomatic treatment.
Grades 3 and 4	Discontinue study treatment.	Not applicable. Any exceptions require medical monitor approval.	Consider initiation of systemic corticosteroids at a dose of 1 to 2 mg/kg per day prednisone or equivalent for severe neuropathies. Institute medical intervention as appropriate for management of severe neuropathy.

Note: See [Appendix B](#) for additional guidance regarding management of neuropathies.

5.4.5.6. Procedures for Immune-Mediated Endocrinopathies

Subjects should be monitored for clinical signs and symptoms of hypophysitis, adrenal insufficiency (including adrenal crisis), and hyper- or hypothyroidism. Subjects may present with fatigue, headache, mental status changes, abdominal pain, unusual bowel habits, and hypotension or with nonspecific symptoms which may resemble other causes such as brain metastasis or underlying disease. Unless an alternate etiology has been identified, signs or symptoms of endocrinopathies should be considered immune-mediated.

Thyroid function tests and clinical chemistries should be monitored at the start of treatment, before each dose, and as clinically indicated based on symptoms. In a limited number of subjects, hypophysitis has been diagnosed by imaging studies through enlargement of the pituitary gland. Recommendations for management of endocrinopathies are shown in [Table 16](#). For additional information on detailed management of asymptomatic TSH elevation versus symptomatic endocrinopathy, see [Appendix B](#).

Table 16: Recommended Approach for Handling Endocrinopathies

irAE	Withhold/Discontinue Nivolumab and Epacadostat	Guidance for Restarting Study Treatment	Supportive Care
Grade 1	No action.	Not applicable.	Provide symptomatic treatment.
Grade 2	May withhold study treatment.	If AE resolves within 4 weeks, subject may restart at the same dose and schedule for epacadostat, nivolumab, and ipilimumab (Treatment Group A) or lirilumab (Treatment Group B). For an AE that does not resolve within 4 weeks, epacadostat should be reduced 1 dose level but nivolumab and ipilimumab (Treatment Group A) or lirilumab (Treatment Group B) may be restarted at the same dose and schedule. If AE does not resolve within 6 weeks, study treatment should be discontinued.	Initiate systemic corticosteroids treatment at a dose of 1 to 2 mg/kg per day of prednisone or equivalent, and initiate appropriate hormone replacement therapy.
Grade 3	Withhold or discontinue study treatment.	If AE resolves or is controlled within 4 weeks, subject may restart at the same dose and schedule for epacadostat, nivolumab and ipilimumab (Treatment Group A) or lirilumab (Treatment Group B). For an AE that does not resolve within 4 weeks, epacadostat should be reduced 1 dose level, but nivolumab and ipilimumab (Treatment Group A) or lirilumab (Treatment Group B) may be restarted at the same dose and schedule. If AE does not resolve within 6 weeks, study treatment should be discontinued.	Consider initiating systemic corticosteroids treatment at a dose of 1 to 2 mg/kg per day of prednisone or equivalent, and initiate appropriate hormone replacement therapy.
Grade 4	Discontinue study treatment.	Not applicable. Any exceptions require medical monitor approval.	Consider initiation of systemic corticosteroids at a dose of 1 to 2 mg/kg per day of prednisone or equivalent, and initiate appropriate hormone replacement therapy.

Note: See [Appendix B](#) for additional guidance regarding management of endocrinopathies.

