1.4.1. Risks From Nivolumab

Overall, the safety profile of nivolumab monotherapy is manageable and generally consistent across completed and ongoing clinical studies, with no MTD reached at any dose tested up to 10 mg/kg. There was no pattern in the incidence, severity, or causality of AEs with respect to nivolumab dose level. The most common adverse reactions ($\geq 20\%$) reported have been fatigue, rash, musculoskeletal pain, pruritus, diarrhea, nausea, asthenia, cough, dyspnea, constipation, decreased appetite, back pain, arthralgia, upper respiratory tract infection, and pyrexia. Most AEs were low grade (Grade 1 to 2) with relatively few related high-grade (Grade 3 to 4) AEs. Infusion reactions are also possible following administration of nivolumab. The safety profile of

nivolumab combination therapy varies with the agent combined with nivolumab but is generally consistent with the safety profiles observed with either agent alone, and in some cases, both frequency and severity of AEs were greater than those observed with either agent alone.

A pattern of immune-related AEs has been defined, including pneumonitis, colitis, hepatitis, endocrinopathies, nephritis and renal dysfunction, skin adverse reactions, and encephalitis, for which management algorithms have been developed; these are provided in [Appendix B](#). Most high-grade events were manageable with the use of corticosteroids, or hormone replacement therapy for endocrinopathies, as instructed in these algorithms. Nivolumab should not be used in subjects with active autoimmune disease, given the mechanism of action of the antibody.

Additional details on the safety profile of nivolumab, including results from other clinical studies, are also available in the [nivolumab IB](#).

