Patients on IV steroids may be switched to an equivalent dose of oral corticosteroids (e.g. prednisone) at start of tapering or earlier, once sustained clinical improvement is observed. Lower bioavailability of oral corticosteroids should be taken into account when switching to the equivalent dose of oral corticosteroids.

Hepatic Adverse Event Management Algorithm

Rule out non-inflammatory causes. If non-inflammatory cause, treat accordingly and continue I-O therapy. Consider imaging for obstruction.

[figure not shown]
Patients on IV steroids may be switched to an equivalent dose of oral corticosteroids (e.g. prednisone) at start of tapering or earlier, once sustained clinical improvement is observed. Lower bioavailability of oral corticosteroids should be taken into account when switching to the equivalent dose of oral corticosteroids.

*I-O therapy may be delayed rather than discontinued if AST/ALT ≤ 8 x ULN and T.bili ≤ 5 x ULN.

**The recommended starting dose for grade 4 hepatitis is 2 mg/kg/day methylprednisolone IV.

Endocrinopathy Management Algorithm

[figure not shown]
Rule out non-inflammatory causes. If non-inflammatory cause, treat accordingly and continue I-O therapy. Consider visual field testing, endocrinology consultation, and imaging.

Patients on IV steroids may be switched to an equivalent dose of oral corticosteroids (e.g. prednisone) at start of tapering or earlier, once sustained clinical improvement is observed. Lower bioavailability of oral corticosteroids should be taken into account when switching to the equivalent dose of oral corticosteroids.

Skin Adverse Event Management Algorithm

Rule out non-inflammatory causes. If non-inflammatory cause, treat accordingly and continue I-O therapy.

[figure not shown]

Patients on IV steroids may be switched to an equivalent dose of oral corticosteroids (e.g. prednisone) at start of tapering or earlier, once sustained clinical improvement is observed. Lower bioavailability of oral corticosteroids should be taken into account when switching to the equivalent dose of oral corticosteroids.

[figure not shown]
*Refer to NCI CTCAE v4 for term-specific grading criteria.

Neurological Adverse Event Management Algorithm

Rule out non-inflammatory causes. If non-inflammatory cause, treat accordingly and continue I-O therapy.

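### Table 16's corticosteroid advice for immune-related endocrinopathy weakens as grade rises, the reverse of Table 10

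*Combined protocol and SAP*

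**What the plan says.** Table 16 sets out supportive care for immune-related endocrinopathy by grade. At Grade 2 the cell reads: "Initiate systemic corticosteroids treatment at a dose of 1 to 2 mg/kg per day of prednisone or equivalent, and initiate appropriate hormone replacement therapy". At Grade 3 it begins "Consider initiating systemic corticosteroids treatment at a dose of 1 to 2 mg/kg per day of prednisone or equivalent", and at Grade 4 "Consider initiation of systemic corticosteroids at a dose of 1 to 2 mg/kg per day of prednisone or equivalent". Hormone replacement is to be initiated at all three grades, so only the steroid verb changes. At Grade 2, withholding study treatment is optional.

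The text above the table covers hypophysitis, adrenal insufficiency (including adrenal crisis) and thyroid events together. It refers sites to Appendix B for "detailed management of asymptomatic TSH elevation versus symptomatic endocrinopathy". The note under the table points there again for "additional guidance regarding management of endocrinopathies". The flowchart for the Appendix B endocrine algorithm is not shown in the public text. What remains is a reminder to rule out non-inflammatory causes, the line "Consider visual field testing, endocrinology consultation, and imaging", and a note on switching from intravenous to oral steroids.

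**The concern.** Guidance on managing toxicity normally becomes firmer, or at least no weaker, as severity increases. Table 16 does the opposite for steroids: it directs them at Grade 2 and only raises them for consideration at Grades 3 and 4, at the same dose. It therefore differs from Table 10 at both levels, being firmer at Grade 2 and weaker at Grades 3 and 4. An investigator who opens both tables for the same subject gets conflicting advice.

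What is at stake is the care of individual subjects. Read alone, the Grade 2 cell gives the table's firmest steroid advice to the mildest grade for which it advises steroids. The Grade 3 and 4 cells give softer advice in a section that names adrenal crisis.

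**Working it through.** No arithmetic applies beyond counting. The check sets the steroid advice in each table of Section 5.4.5 side by side. Doses are prednisone equivalents in mg/kg per day.

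| Table | Grade 2 | Grades 3 and 4 | Change with grade |
|---|---|---|---|
| 10, general | Consider; no dose | Indicated; 1 to 2 may be used | Firmer |
| 11, pneumonitis | Indicated; no dose | Indicated; no dose | Same |
| 12, enterocolitis | 0.5 to 1, if symptoms last over 1 week | Start 1 to 2 | Firmer |
| 13, hepatitis | 0.5, if elevation lasts over 1 week | Start 1 to 2 | Firmer |
| 14, dermatitis | Topical or systemic, if not improved in 1 week; no dose | Give 1 to 2 | Firmer |
| 15, neuropathy | Consider; no dose | Consider 1 to 2 | Same verb, dose added |
| 16, endocrinopathy | Initiate 1 to 2, no condition | Consider 1 to 2 | Weaker |

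The advice is firmer at higher grades in four tables (10, 12, 13, 14), keeps the same verb in two (11, 15) and is weaker in one (16): 4 + 2 + 1 = 7. Section 5.4.5.7, on other immune-mediated reactions, also directs 1 to 2 mg/kg per day for severe events.

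Two features that look unusual in Table 16 need separating:

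- **Steroids at Grade 2 without a waiting period.** This is not unique, because Table 11 does the same for pneumonitis.
- **1 to 2 mg/kg per day named at Grade 2.** This is unique to Table 16. Five of the other six tables (10 and 12 to 15) name that dose, and only at Grades 3 and 4.

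The direct conflict is with Table 10, since it applies to immune-related events in general:

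- **Grade 2:** Table 10 says consider; Table 16 says initiate.
- **Grades 3 and 4:** Table 10 says indicated; Table 16 says consider.

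**The case against.** The best defense is that endocrine events differ from other immune-related events and are often managed by replacing the missing hormone. Section 1.4.1 says: "Most high-grade events were manageable with the use of corticosteroids, or hormone replacement therapy for endocrinopathies, as instructed in these algorithms". That gives some support for a softer steroid verb at Grades 3 and 4, and Table 15 uses the same verb at those grades. It does not explain why Grade 2 should be firmer than Grades 3 and 4, because Table 16 already directs hormone replacement at all three grades.

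A second objection is that the documents do not show which cell is in error. Grade 2 may be too strong, Grades 3 and 4 too weak, or both. This stands, and the correction must therefore cover both ends. It also means that softening the Grade 2 verb for suspected hypophysitis or adrenal insufficiency needs medical confirmation.

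A third objection is that the table does not act alone. It is titled a recommended approach, Section 5.4.5 asks that events of Grade 2 or above be discussed with the sponsor immediately, and Appendix B is cited for the symptom distinction. These points limit the consequence but leave the contradictory wording in the protocol body.

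Two stronger readings are tempting, and the documents support neither:

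- **The plan orders high-dose steroids for every Grade 2 thyroid event, including a raised TSH without symptoms.** The section refers that distinction to Appendix B, and the flowchart is missing only from the public text. On the fallback severity scale in Section 8.1.2, used where CTCAE does not classify an event, asymptomatic findings needing no intervention are Grade 1 and would not reach this row.
- **Subjects would receive some multiple of the proper Grade 2 dose.** The only other Grade 2 doses are for bowel and liver, the Table 12 range meets Table 16's at 1 mg/kg, and nothing says that endocrine dosing should match either.

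**Conclusion.** The point holds as an inconsistency of wording in safety guidance: Table 16's steroid advice weakens from Grade 2 to Grades 3 and 4 and conflicts with Table 10 at each of these grades. This rests on the text alone and does not depend on what the Appendix B flowchart shows.

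The practical effect is small. Section 4.1 states that enrollment is closed and that no subject entered Treatment Group B, so only Group A subjects still on treatment are affected. The dose-limiting toxicity definition, the endpoints and the planned analyses are unchanged. The summary of immune-related events in Section 9.4.2.5 is not broken down by steroid use.

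The documents do not give the frequency of Grade 2 endocrinopathy on this triplet, so the number of subjects affected cannot be estimated. Whether any subject would be over- or undertreated depends on the Appendix B algorithm and on the discussion with the sponsor.

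**What to change.** Reword the supportive-care column of Table 16.

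- **Grade 2:** initiate hormone replacement as appropriate. Consider systemic steroids at 1 to 2 mg/kg per day (prednisone equivalent) for symptomatic suspected hypophysitis or adrenal insufficiency. Manage isolated thyroid events, including raised TSH without symptoms, according to Appendix B.
- **Grades 3 and 4:** make the steroid wording no weaker than at Grade 2 and consistent with Table 10, and keep the direction to initiate hormone replacement.

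Before issue, the medical monitor should confirm the text against the Appendix B endocrine algorithm. If that algorithm directs steroids for symptomatic hypophysitis or adrenal insufficiency, the firmer verb should stay for those conditions at Grade 2, and Grades 3 and 4 should be at least as firm.

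The cost is a small medical review, edits to one table and a clarification letter to sites. Data collection and analysis do not change.
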